4.2 Analysis methods

4.2.1 Analyses of study population

4.2.1.1 Patient disposition

The reason for screen failure (i.e., patients screened but not randomised) will be listed.

The number and percentage of patients enrolled, randomised, receiving IP, completing the study and prematurely discontinuing from the study (as recorded on the End of Study eCRF page), including the reasons for premature discontinuation, in addition to the number of patients included in each analysis set, will be summarised overall and by treatment for enrolled patients.

The number and percentage of patients completing the treatment period and prematurely discontinuing during the treatment period, including the reasons for premature discontinuation, will be summarised by treatment for the FAS. For patients who discontinue from the study, the discontinuation will be assigned to the last treatment period prior to their discontinuation. Patients who do not discontinue during a treatment period will be as counted as completing the treatment period.

A summary of important protocol deviations will be provided. Important protocol deviations will be listed by centre and treatment.

4.2.1.2 Demographic and baseline characteristics

Analyses of demographic and baseline characteristics will be performed on the FAS.

Standard descriptive statistics will be presented for the continuous variables of:

- Age (years)
- Weight (kg)
- Height (cm)
- BMI (kg/m²), calculated as follows (where height is in metres): $\frac{\text{weight}}{\text{height}^2}$
- Time from diagnosis of COPD to randomisation (years), calculated as:

$$\frac{\text{date of randomisation} - \text{date of diagnosis of COPD}}{365.25}$$

- Time from most recent exacerbation to randomisation (months), calculated as:

$$\frac{\text{date of randomisation} - \text{date of most recent exacerbation}}{30.4}$$

- Number of exacerbations in previous 12 months
- Pre-bronchodilator FEV₁ at screening (L)
- Pre-bronchodilator FEV₁ % predicted at screening
- Pre-bronchodilator FVC at screening (L)
- Pre-bronchodilator FVC % predicted at screening
- Post-bronchodilator FEV₁ at screening (L)
- Post-bronchodilator FEV₁ % predicted at screening
- Post-bronchodilator FVC at screening (L)
- Post-bronchodilator FVC % predicted at screening
- Post-bronchodilator FEV₁/FVC (%) at screening
- FEV₁ absolute reversibility at screening (mL)
- FEV₁ percentage reversibility at screening

The total counts and percentages of patients will be presented for the categorical variables of:

- Age categorized (18-64 years, 65-84 years, 85 years and older)
- Country
- Sex
- Race
- Ethnicity
- Smoking status (Current smoker, Former smoker)
- Smoking history (number of pack-years)
- Severity of airflow limitation at screening, defined as:

- Stage II (moderate): post-bronchodilator FEV₁/FVC < 70% and post-bronchodilator FEV₁ % predicted ≥ 50% and < 80%
- Stage III (severe): post-bronchodilator FEV₁/FVC < 70% and post-bronchodilator FEV₁ % predicted ≥ 30% and < 50%
- Reversible at screening (Yes, No). A patient is defined as being reversible if the post-salbutamol spirometry increases (post-bronchodilator FEV₁) with at least 12% (percentage reversibility) and at least 200 mL (absolute reversibility) compared to the pre-salbutamol spirometry.

Medical history will be listed and the number and percentage of patients with any relevant medical history will be summarised overall, by SOC and PT. Surgical history will be listed and summarised similarly.

The following summaries will be produced:

- Summary of prior medications received (15 days prior to signing the ICF), by ATC level 3 code and PT, overall. Prior medications that continue after the date of first dose will be reported as well and classified in both prior and concomitant medication groups..
- Summary of disallowed medications will be reported.

Additionally, a subset of the previous summary will be produced presenting the number and percentage of patients who used any prior medication for COPD by the following therapeutic categories; Inhaled Corticosteroids (ICS), Long-Acting Beta2-Agonists (LABA), LABA+ICS combination, Long-Acting Muscarinic Antagonist (LAMA), Short-Acting Beta2-Agonists (SABA), SABA+ICS combination, Short-Acting Muscarinic Antagonist (SAMA), SABA+SAMA combination, Influenza Vaccine, Oxygen, Xanthines and PDE4 inhibitors. If a patient has LABA+ICS followed by ICS (as monotherapy), then this patient will be counted only once in the LABA+ICS category.

Multiple records for a patient in the same ATC level 3 category and PT will be counted only once.

All concomitant and other treatment data will be listed.

4.2.1.3 Exposure

Treatment duration (days) will be summarised by treatment for the SS, using descriptive statistics.

4.2.1.4 Treatment compliance

Treatment compliance (%) will be summarised by treatment for the FAS, using continuous type descriptive statistics.

Treatment compliance will also be presented using the following compliance status categories: <70%, >=70%-130%, >130%.

4.2.2 Analysis of the primary variable: change from baseline in Trough FEV₁ at Day 15

All analyses will be based on the FAS and P-PS populations.

The primary efficacy variable will be analysed by means of a mixed model: fixed effects for treatment, sequence, and period and random effect for patient (nested within sequence), the pre-dose FEV₁ of each period being included as covariate.

Each treatment effect and treatment differences will be estimated by the Least Square means along with their standard errors (SE) and 95% CI, and the p-value corresponding to the between-treatment group difference. Differences between least squares means, the SE of the difference, 95% CIs, and the p-values corresponding to between-treatment differences will also be presented for each comparison of interest.

The main treatment comparisons that will be evaluated are:

- AZD8871 600 µg versus Anoro[®] Ellipta[®]
- AZD8871 600 µg versus Placebo

A treatment comparison for Anoro[®] Ellipta[®] versus placebo will also be explored.

A sensitivity analysis will be performed using as baseline FEV₁ the mean of the 2 measured values prior to the morning IP administration on Day 1 of the first treatment period (see Section 3.1 for the baseline FEV₁ derivation on Day 1 of the first treatment period in case of missing value). This sensitivity analysis will be performed by means of a mixed model: fixed effects for treatment, sequence, and period and random effect for patient (nested within sequence), the pre-dose FEV₁ of the first period being included as a covariate to capture carry-over effects.

For all mixed models, the estimation method used will be Restricted Maximum Likelihood (REML). The Kenward and Roger method for computing degrees of freedom will be used.

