9.2 Sample size determination

The study will be powered to demonstrate superiority of AZD8871 600 µg versus Anoro[®] Ellipta[®] for the primary efficacy endpoint. With a total of 54 patients, there is 90% power to detect a difference between AZD8871 and Anoro[®] Ellipta[®] treatments for the change from baseline to Trough FEV₁ at Day 15 equal to 100 mL, assuming a SD of differences of 220 mL, 2-sided 5% significance level and a normal distribution. Assuming an approximate 25% dropout, the total sample size will be approximately 72 (multiple of 6 sequences). From previous studies, the screening failure rate is estimated to be approximately 50%; therefore approximately 145 screened patients will be required to achieve the goal of approximately 72 randomised patients.

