9.4.1 Efficacy analyses

The analysis of all efficacy variables will be performed on the FAS population. In addition, the primary efficacy variable will also be analysed using the PP population, and on the FAS population with a model including covariates to capture potential carry-over effects.

Analysis of the primary efficacy variable

The primary efficacy variable is the change from baseline in Trough FEV₁ at Day 15 (ie, after 14 days of treatment).

Baseline for FEV₁ will be defined as the mean of the 2 measured values for the corresponding variable (2 measurements 45 min apart, at -1 hour and -15 min), prior to the morning IP administration on Day 1 of each treatment period. If both are missing, the Visit 2 pre-bronchodilator value will be used instead.

Trough is defined as the mean of the FEV₁ values obtained at 23 hours and 23 hours and 45 min after the IP administration on Day 1 and Day 14 (ie, obtained on Day 2 and Day 15). On Day 8, Trough is defined as the mean of the FEV₁ pre-dose values (-1 hour and -15 min). If 1 of the values is missing, the available value will be used as Trough.

This variable will be analysed by means of a mixed model with fixed effects for treatment, sequence, and period. The patient will be fitted as a random effect and the pre-dose FEV₁ of each period will be included as a covariate.

Each treatment effect and treatment differences will be estimated by the Least Square (LS) means along with their SE and 95% CI, and the p-value corresponding to the between-treatment group difference.

The main treatment comparisons that will be evaluated are:

- AZD8871 600 µg versus Anoro[®] Ellipta[®].
- AZD8871 600 µg versus Placebo.

A treatment comparison for Anoro[®] Ellipta[®] versus placebo will also be explored.

A sensitivity analysis will be performed for the primary efficacy variable; computing the baseline for FEV₁ as the mean of the 2 measured values for the corresponding variable (2 measurements 45 min apart, at -1 hour and -15 min), prior to the morning IP administration on Day 1 of the first treatment period. If both are missing, the Visit 2 pre-bronchodilator value will be used instead.

This “modified” primary efficacy variable (change from first period baseline in trough FEV₁) will be analysed by means of a mixed model; a random effects model with fixed effects for treatment, sequence, and period. The patient will be fitted as a random effect and the pre-dose FEV₁ of first period will be included as a covariate.

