4.2.3 Analysis of the FEV₁-related secondary variables

- Change from baseline in Trough FEV₁ on Day 2, and Day 8
- Change from baseline in Peak FEV₁ on Day 1, Day 8, and Day 14

The analyses of the above endpoints will be performed using the FAS and will be based on the same model as described in 4.2.2.

- Change from baseline in Trough FEV₁ over treatment duration (Day 1 to Day 15)
- Change from baseline in Peak FEV₁ over treatment duration (Day 1 to Day 14)

The analyses of the 2 above endpoints will be performed using the FAS. These 2 efficacy variables will be analysed by means of a mixed repeated model: fixed effects for treatment, sequence, period, and day as a repeated factor within period (Day 1, Day 8 and Day 15 (Day 14 for Peak FEV₁)) and day-by-treatment interaction; a random effect for patient (nested within sequence) will be included also. The repeated covariance structure for day will be compound symmetry; the pre-dose FEV₁ of each period being included as a covariate.

For all mixed models, the estimation method used will be Restricted Maximum Likelihood (REML). The Kenward and Roger method for computing degrees of freedom will be used. The same treatment comparisons as those for the primary variable will be performed for the secondary variables.

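### The primary model's single period-baseline covariate forces one slope between and within patients; splitting it could tighten the treatment contrast modestly at almost no cost

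*SAP*

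**What the plan says.** Protocol 9.4.1 defines the response: "The primary efficacy variable is the change from baseline in Trough FEV₁ at Day 15". Baseline is the mean of the two pre-dose readings on Day 1 of the same period, so each period's baseline is subtracted in full.

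SAP 4.2.2 fits "fixed effects for treatment, sequence, and period and random effect for patient (nested within sequence"), with the pre-dose FEV₁ "of each period being included as covariate". Protocol 9.4.1 has the same covariate: the pre-dose FEV₁ "of each period will be included as a covariate". Estimation is by REML with Kenward–Roger degrees of freedom. SAP 4.2.3 carries the covariate into the repeated-measures models ("of each period being included as a covariate"), and the remaining FEV₁ analyses in 4.2.3 and 4.2.4 refer back to 4.2.2.

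Nothing in either document separates the patient's average baseline from the period's deviation from it:

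- The sensitivity analysis uses only the first-period baseline, one value per patient, so it contains no within-patient slope.
- The protocol's carry-over model does not name its covariates.
- The freedom to alter covariates in protocol 9.4.1 is given for the secondary variables only.
- SAP section 6 does not mention the point.

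On sample size, protocol 9.2 states: "With a total of 54 patients, there is 90% power to detect a difference" in the change to trough FEV₁ "at Day 15 equal to 100 mL", with an SD of differences of 220 mL. SAP 1.3 gives 220 mL without saying that it is the SD of differences.

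**The concern.** AZD8871 is compared with Anoro Ellipta within patients, so only the within-patient relation between baseline and change can sharpen that contrast. That relation differs from the one between patients. A patient whose pre-dose FEV₁ happens to be high in one period tends to show a smaller change in that period. A patient whose FEV₁ is generally high has little reason to show a smaller change than anyone else. A raw time-varying covariate with a random intercept gives both relations one coefficient, and the larger between-patient spread dominates it.

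What is at stake is the width of the interval for the primary contrast and for the FEV₁ analyses that reuse the model. SAP 4.1.1 puts estimation ahead of testing, so interval width matters here.

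**Working it through.** **The plan's own figure.** With difference 100 mL, SD of differences 220 mL and two-sided 5%:

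- Normal formula: (1.960 + 1.282)² × 220²/100² = 50.9, so 51 patients.
- Paired t formula: 53 patients for 90% power; at 54, power is 0.906.
- Randomised: 54/0.75 = 72.

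The stated figures reproduce.

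**Assumed inputs.** The between-patient SD (B), within-patient SD (s) and within-patient baseline–trough correlation (r) are not in the documents. I take equal within-patient SD for baseline and trough, and calibrate s to the plan. The variance of the difference between two change scores is 4s²(1−r) = 220², so s = 110/√(1−r). At r = 0.5, s = 155.6 mL and s² = 24,200.

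**Slopes of change on baseline**, for B = 400 mL and r = 0.5, three periods per patient and no patient-level variation in response:

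- Within patient: −(1−r) = −0.50.
- Between patients (on patient means): −[s²(1−r)/3]/(B² + s²/3) = −4,033/168,067 = −0.024.
- Pooled, weighting by sums of squares per patient (2s² = 48,400 within; 3 × 168,067 = 504,200 between): (−24,200 − 12,100)/552,600 = −0.066.

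REML fits to simulated trials give about −0.08, close to this approximation.

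**Effect on the SE.** For 54 completers and a fitted slope b, the SE of the contrast is approximately √{2s²[1 + (1+b)² − 2r(1+b)]/54}:

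| Analysis | b | SE by formula (mL) | SE in simulation (mL) |
|---|---|---|---|
| Plain change score | 0 | 29.9 | – |
| Planned single slope | −0.08 | 28.8 | 28.2–28.6 |
| Separate within-patient slope | −0.50 | 25.9 | 25.7–26.0 |

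The planned model therefore sits close to a change-score analysis, and splitting the slope gains about 9% in SE. By normal approximation, an SE of 28.4 gives power Φ(100/28.4 − 1.96) = 0.94 and an SE of 25.8 gives 0.97. Both exceed the stated 90%.

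**Two design features reduce the gain.**

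- The FEV₁ stability check (protocol 8.1.2, SAP 1.2) requires later-period baselines to lie within 20% or 200 mL of Visit 3. Read as the wider limit, with mean FEV₁ assumed at 1,500 mL, it cuts the baseline SD at r = 0.5 from 156 to about 115 mL. At r = 0.8, 38–40% of later-period baselines would fail it.
- About 25% dropout leaves some patients with one or two periods. Dropout alone does not remove the gain.

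With both included and B = 300–500 mL:

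| r | Fall in mean SE from splitting the slope |
|---|---|
| 0.3 | about 9–12% |
| 0.5 | about 3–6% |
| 0.7–0.8 | about 0–2% |

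Neither model was biased, and the mean SE did not rise in any setting. In single simulated trials at r = 0.7 with the stability check, the split model's SE was slightly larger in about 22–33%.

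**Where the effect fades.**

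- *Patient-level response.* For completers without the stability check, B = 250 mL and a 250 mL SD for a response shared across all three treatments let the planned model keep 77–87% of the within-patient slope. The gain is then at most about 2%.
- *Unequal variances.* The within-patient slope is r × (trough SD/baseline SD) − 1. Holding the paired SD at 220 mL and r = 0.5, a baseline SD of 100 mL implies a trough SD of 179 mL. The slope is 0.5 × 1.79 − 1 = −0.10 and the largest possible gain is 0.2%. At 120 mL the trough SD is 176 mL, the slope is −0.27 and the limit is about 2%.

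**The case against.** The strongest reply is that nothing planned fails. The comparison is unbiased. On protocol 9.2's own terms the planned model has at least the stated power. The study is exploratory, and the size of any gain rests on quantities that the documents do not report. The stability check limits the very spread that the fix exploits. All of that stands, and it makes this an optional improvement. It does not remove the mechanism, which follows from the model as written.

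Three stronger readings are tempting and should be resisted:

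- *The plan collects period baselines and then ignores them.* It does not: each is subtracted in full in the response. Only the further regression correction is weakened.
- *The primary comparison is underpowered.* If 220 mL were an SD after within-patient baseline adjustment, single-slope power would be about 0.69 to 0.90 for r from 0 to 0.75 (B = 500 mL). Protocol 9.2 does not say that. It describes an SD of differences for the change from baseline. SAP 1.3's shorter wording is looser but does not point to an adjusted SD.
- *Up to a quarter of the SE is lost.* Gains of 26–27% arise only at r = 0 with complete data and no stability check.

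The protocol's latitude on covariates answers the point for secondary variables but does not reach the primary one.

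**Conclusion.** The concern holds as a modest, avoidable loss of precision. With wide between-patient differences in FEV₁, the single covariate gives the treatment contrast little of the within-patient correction. The gain forgone, 3–6% of the SE at r = 0.5, is equivalent to about 6–13% more patients (1/0.97² = 1.06; 1/0.94² = 1.13). It is larger at low r and near zero when r or the shared patient-level response variation is high. These sizes depend on the assumed between-patient SD of 300–500 mL, equal within-patient variances, about 25% dropout and the wider reading of the stability limits. Validity and the stated power are not in question.

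**What to change.** In SAP 4.2.2, and by reference in 4.2.3 and 4.2.4, add the patient's mean pre-dose FEV₁ over the periods attended as a second covariate beside the period pre-dose FEV₁. Entering the patient mean and the period's deviation from it is equivalent. Leave the treatment, sequence, period and random patient terms, REML and Kenward–Roger as they are. Record the change for the primary model in SAP section 6 before unblinding. It would also help for SAP 1.3 to say, as protocol 9.2 does, that 220 mL is the SD of differences.

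The cost is one SAP sentence, one derived variable and one between-patient degree of freedom. No new data are needed. A patient with a single period has zero deviation and adds nothing to the within-patient slope, which does no harm.

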8.1.2 FEV₁ and clinical stability check

This is not an outcome measure. FEV₁ stability check will be performed at Visits 6 and 9 (Day 1 of treatment periods 2 and 3). FEV₁ stability check will be based on the pre-BTR values. FEV₁ at these visits will be calculated as the mean of the 2 pre-dose values and compared with the mean of the pre-dose FEV₁ values measured at Visit 3. This should be within (\pm)20% or (\pm)200 mL compared to the pre-dose FEV₁ (mean of the 2 measured values) of the first treatment period (Visit 3). If the FEV₁ stability criterion is not met, an additional

measurement could be taken within 30 min of the second pre-dose measurement, and the mean of the last 2 measurements will be considered for the FEV₁ stability criterion.

If the FEV₁ stability criterion is still not met, the test can be rescheduled as soon as possible (up to a maximum of 3 times), and if the FEV₁ stability criterion is not met after re-testing, the patient should be withdrawn.

Patient's clinical stability will be assessed at Visit 2 and before the start of each treatment period and defined as follows:

- No relevant respiratory signs/symptoms that modify the patient's baseline daily activities.
- Not meeting the criteria of COPD exacerbation (as per Investigator's clinical judgment).
- No ongoing SAEs.
- No relevant AEs that potentially modify the absorption, distribution, metabolism, and excretion of IP.

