- t_{\max} and t_{last} will be presented as received in the data, usually to 2 decimal places
- AUC_{last} , $AUC_{(0-24)}$, C_{avg} , accumulation ratios and metabolite to parent ratios and %Fluc and will be presented to 3 significant figures

For concentration data all descriptive statistics will be presented to 4 significant figures with the exception of the minimum and maximum which will be presented to 3 significant figures. For PK parameter data the descriptive statistics will be presented according to the following rules:

- C_{\max} , AUC_{last} , $AUC_{(0-24)}$, C_{avg} , Rac ratios, metabolite to parent ratios and %Fluc descriptive statistics will be presented to 4 significant figures with the exception of the minimum and maximum which will be presented to 3 significant figures
- t_{\max} and t_{last} all descriptive statistics will be presented as received in the data, usually to 2 decimal places

PK concentration and parameter data for patients excluded from the PKs will be included in the data listings, but not in the descriptive or inferential statistics or in mean figures or combined individual figures.

Individual plasma concentrations versus actual elapsed time after dose will be plotted on both linear and semi logarithmic scales for AZD8871 and LAS191861 separately with the Day 1 and Day 14 data overlaid on the same plot. Combined individual plasma concentrations will be presented on both linear and semi logarithmic scales with separate plots for each analyte and PK day (Day 1 and Day 14).

Figures for the gmean concentration-time data (with gSD error bars) will be presented, on both a linear and semi-logarithmic scales by analyte, with Day 1 and Day 14 overlaid on the same plot.

To evaluate any potential carryover effect in the study due to AZD8871 treatment, Day 1 predose concentrations for AZD8871 and LAS191861 in those periods preceded by AZD8871 treatment will be also listed. These data however, will not be summarized.

4.3.1.2 Statistical analysis of accumulation in AZD8871 exposure (C_{\max} and $AUC_{(0-24)}$) following multiple doses

$AUC_{(0-24)}$ and C_{\max} at Day 1 and Day 14 will be analysed by means of a linear mixed-effect model with the logarithm of the PK parameters as the response variable and sequence, period,

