5. INTERIM ANALYSES (NOT APPLICABLE)

6. CHANGES OF ANALYSIS FROM PROTOCOL

Change in the analysis set used:

All demographic and baseline characteristics will be analysed using the full analysis set instead of the safety population.

Change in definition of baseline for vital signs, laboratory variables including i-STAT glucose and potassium and ECG variables:

Baseline is defined as the last assessment made before the first dose of IP in each period instead of the value obtained prior to the morning IP administration on day 1 of Visit 3

For HR, and QTcF parameters:

Analyses of change from baseline at each day and timepoint within day will be performed instead of the analysis of AUC₀₋₄ at Day 1, Day 8, and Day 14 and AUC₀₋₂₄ at Day 1 and Day 14. No formal analysis of other ECG parameters will be performed.

Dropouts due to lack-of-efficacy during treatment periods added as a COPDCompEx event.

Additional analysis on FEV1:

Statistical analyses on the change from baseline in FEV1 15 min, 30 min, 1, 2, 4, 8, 23, and 23:45 hours post-dose will be presented by treatment group at Day 1 and Day 15.

Also, analyses on the change from baseline in FEV1 15 min, 30 min, 1, 2, and 4 hours post-dose will be presented by treatment group at Day 8.

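### The SAP's carry-over covariate is measured before any study drug and cannot capture carry-over; the carry-over model planned in the protocol is absent and the change is undeclared

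*SAP*

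**What the plan says.** Protocol 9.4.1 plans the primary variable on the FAS, on the per-protocol population, and also "on the FAS population with a model including covariates to capture potential carry-over effects". It does not name those covariates. Later in the same section, in its own paragraphs, it describes a sensitivity analysis that replaces each period's baseline by the Period 1 baseline, where the pre-dose FEV1 of the "first period will be included as a covariate". No carry-over purpose is stated there.

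SAP 4.2.2 has the primary model (treatment, sequence, period, random patient, period-specific pre-dose FEV1) on the FAS and per-protocol sets, plus the first-period-baseline analysis. It ends the description of the latter with the pre-dose FEV1 "of the first period being included as a covariate to capture carry-over effects". The same section says this baseline is measured "prior to the morning IP administration on Day 1 of the first treatment period". No efficacy model in the SAP contains a term for the treatment given in the preceding period.

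SAP Section 6 lists changes from the protocol. It records that the ECG AUC analyses are replaced and that "No formal analysis of other ECG parameters will be performed". It says nothing about a carry-over model.

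**The concern.** A covariate can adjust for carry-over only if it varies with what the patient received in the preceding period. The Period 1 pre-dose value precedes all study treatment and is the same number in all three of a patient's periods. It therefore carries no information on preceding treatment, and the model has no term that estimates, tests or removes carry-over into the trough.

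Two things are at stake. A reader of the study report will take this analysis as carry-over-adjusted when it is not. And an analysis the protocol announced disappears without being listed as a change. The trial relies on a 42 to 49 day wash-out (Protocol 4.2) to exclude carry-over, and the protocol's extra model was the planned check of that assumption on FEV1.

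**Working it through.** **Inputs.** Six sequences of Protocol Table 4; 54 completers, taken as 9 per sequence; SD of differences 220 mL, effect 100 mL and two-sided 5% (Protocol 9.2). The documents give no carry-over size, so all sizes below are assumed.

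**1. The plan's own figure.** SE of a treatment difference = 220/√54 = 29.94 mL. Power = Φ(100/29.94 − 1.96) = 0.916, or 0.906 with the t distribution. Allowing for dropout, 54/0.75 = 72. The stated 90%, 54 and 72 reproduce and are not in dispute.

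**2. What the covariate does.** With complete data, the treatment contrasts are within-patient differences. A value that is constant within a patient cancels from each of them. In simulated data with 54 completers, removing the covariate changed the AZD8871-Anoro estimate by less than 1e-10 mL. With 72 randomised and 18 dropouts (9 after Period 1, 9 after Period 2) it changed it by 0.2 mL on average and at most 3.9 mL in 40 runs.

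**3. Bias left in the model.** Write T = AZD8871, A = Anoro, P = placebo. Table 4 gives TAP, TPA, ATP, APT, PTA, PAT. Each treatment occurs twice in every period, so T−A is the mean under T minus the mean under A. Let AZD8871 add L mL to the next period's trough.

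- A follows T in 2 of 6 sequences (TAP, PTA): mean contamination L/3.
- P follows T in 2 of 6 sequences (TPA, ATP): mean contamination L/3.
- T never follows T: contamination 0.

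The bias is therefore −L/3 for both T−A and T−P. For L = 10, 30, 60 or 100 mL this is −3, −10, −20 or −33 mL. If Anoro also carries over by L, it adds L/3 to T (ATP, PAT) and L/3 to P (TAP, APT). T−A is then unbiased, and T−P still has −L/3.

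**4. With a preceding-treatment term.** Exact least squares on the same design gives bias 0 in all these cases. The variance of a treatment contrast rises from 2σ²/54 to 2.5σ²/54, where σ² = 220²/2 = 24,200. The ratio is 1.25 and the SE is 29.94 × √1.25 = 33.47 mL. The AZD8871-versus-Anoro carry-over contrast has variance 4.5σ²/54, so its SE is √(4.5 × 24,200/54) = 44.9 mL. The size detectable with 80% power is 2.80 × 44.9 = 126 mL.

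**5. Simulation as illustration.** Mean AZD8871−Anoro estimate in mL, truth 100, 2,500 REML runs per row, Monte Carlo SE 0.6 to 0.7. Assumed between-patient SD 480 mL and within-patient baseline-trough correlation 0.5; AZD8871-only carry-over.

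| Carry-over in baseline / trough (mL) | SAP primary | SAP first-period baseline | Preceding-treatment model |
|---|---|---|---|
| 60 / 60 | 99 | 81 | 100 |
| 60 / 30 | 108 | 90 | 100 |
| 60 / 0 | 119 | 100 | 100 |
| 0 / 60 | 80 | 80 | 100 |
| 30 / 30 | 99 | 91 | 101 |

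The primary column depends on the assumed variances and correlations. Varying the between-patient SD (300 or 480), the within-patient correlation (0 or 0.5) and the between-patient baseline-trough correlation (0.9 to 1), with 250 runs per setting and Monte Carlo SE about 2, moved it to about 91-100 in the first row and 101-110 in the second. The first-period-baseline column was stable. In the dropout runs of step 2, with carry-over 60 / 60, that analysis averaged 84.

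**The case against.** The protocol never names its carry-over covariates. The SAP authors may have read the two protocol items as one, and a preceding-treatment model is then a proposal, not a text to be restored. This stands as a caveat. Separate statements and the plural make two analyses the natural reading, and a merged analysis would still not do what its label says.

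The first-period baseline is also not useless. It keeps contaminated Period 2 and 3 baselines out of the change score, as the 60 / 0 row shows (119 against 100), and comparing it with the primary result gives an informal hint of carry-over. That is right, but the benefit comes from the baseline definition, not from the covariate, and it does not reach the trough.

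Carry-over into the trough may well be small. The next Day 15 trough falls at least 42 + 14 = 56 days after the last dose, so a waning effect would contaminate the trough no more than the baseline. The 0 / 60 row is then implausible and the equal rows are upper bounds. This is fair, and the bias figures are conditional on carry-over existing. The wrong label and the undeclared change do not depend on its size.

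Other checks exist. The FEV1 stability rule at Visits 6 and 9 (within 20% or 200 mL, Protocol 8.1.2) is a coarse entry rule of which the protocol says "This is not an outcome measure". Day 1 pre-dose concentrations after AZD8871 are available only in the PK subset, and SAP 4.3.1.1 says "These data however, will not be summarized". Neither estimates carry-over on FEV1.

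Finally, this is one supportive analysis in an exploratory Phase IIa study, and the adjusted model is imprecise. Both points are true. They limit the weight of the finding and argue for reporting an interval, not for keeping a wrong description.

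**Conclusion.** The concern holds and should be fixed. The covariate cannot capture carry-over, no SAP efficacy model does, and Section 6 does not declare the difference from Protocol 9.4.1. The exact result is a bias of −1/3 mL per mL of AZD8871-only trough carry-over in both main comparisons. It assumes first-order carry-over and the balanced design with complete data. The actual size cannot be found from the documents and may be nil. Which of the two SAP analyses is less biased depends on how carry-over divides between baseline and trough, so their agreement or disagreement cannot settle the matter. The choice of primary analysis, the 54 completers and the stated power are unchanged.

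**What to change.** 1. In SAP 4.2.2, delete the carry-over clause from the first-period-baseline analysis and keep that analysis as a sensitivity analysis to the baseline definition.
2. Add a separate FAS sensitivity model: the primary mixed model plus a fixed effect for the treatment in the preceding period (none, AZD8871, Anoro, placebo). The level 'none' coincides with Period 1, so two carry-over contrasts are estimable. Report these and the adjusted treatment contrasts with 95% CIs.
3. Declare any remaining difference from Protocol 9.4.1 in SAP Section 6.

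The cost is one extra model, a wording change and one line. In that model only, the treatment SE rises from 29.9 to 33.5 mL, which is normal-approximation power Φ(100/33.47 − 1.96) ≈ 85% instead of about 92%. With an SE near 45 mL, the carry-over contrast should be read as an estimate with its interval. A non-significant result must not be taken as proof that the wash-out was sufficient, nor used to choose between models.
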